STUDY PROTOCOL

QUANTIFICATION OF DICLOFENAC 2.32 % (VOLTAREN) IN RINSE WATER AFTER DIFFERENT APPLICATION METHODS

Sponsor Name and Legal Registered Address	Haleon (UK) [name]
Sponsor contact	PPD
Sponsor study no./ order no.	300272
Study site	SGS proderm GmbH, Schenefeld/Hamburg, Germany
Principal Investigator	Dr. rer. nat. [name], Manager Study Operations / Investigations
Investigator	PPD
CCI	
Test date(s)	March 26 to April 11, 2025

OBJECTIVE

The aim of the exploratory study is to quantify the amount of diclofenac in rinse water after application of the test product containing 23,2 mg/g Diclofenac-N-Ethylethanamin (Voltaren® Schmerzgel forte; 2,32 %) either by hand or using an applicator and subsequent washing and/or wiping.

For this study female and male participants with healthy skin on the elbows and hands will be enrolled. The amount of diclofenac in the water will be assessed after three different washing methods, with and without use of an applicator in a cross over design.

The study will be reviewed by an independent institutional review board (IRB) for ethical approval.

ASSESSMENT

The following assessment(s) will be performed:

- Voltaren® Schmerzgel forte; 2,32 % (Diclofenac) in water [mg/l]
- Amount of test product residues by gravimetrical measurements [mg]

TYPE OF PRODUCT(S)

- Voltaren® Schmerzgel forte; 2,32 % with and without applicator (Pain Gel (Medicinal Product))

STUDY DESIGN

- Exploratory
- Open labeled
- Cross over

TYPE OF STATISTICS

- Comparison between all water samples
- Descriptive statistics for all water samples

ASSESSMENT TIMES

After test product application and washing for Diclofenac concentration:

Method 1 = W01 (Hands), W02 (Elbow)

Method 2 = W03 (1st washing of elbow), W04 (2nd washing of elbow)

Method 3 = W05 (Hands and elbow)

For amount of test product residues by gravimetric measurements:

Method 3

TEST MATERIALS

Code/Study site	Product/Code/Sponsor/Concentration
A	Voltaren® Schmerzgel forte with and without Racetrack applicator

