- apply any products with the same indication as the test product to the test area throughout the entire course of the study

The participants will be instructed to...

- Not applicable

INFORMED CONSENT

For studies with participants the following procedure will be effective: Each participant must provide the investigator/investigator's designee with written informed consent prior to enrollment in the study. The participants will be provided with a signed copy of the informed consent statement.

The original signed copy for each participant in the study will be retained in the investigator's study records. The consent statement shall meet the requirements of any applicable regulation. The investigator or the investigator's designee will inform each participant as to the purpose and nature of the study in compliance with applicable regulations.

The participants are informed that they can withdraw their consent at any time and that they can stop their participation in this study at any time, without disadvantages. They are also informed that the study site can also prematurely terminate their participation in the study, for example for administrative reasons.

[figure not shown]
TEST PROCEDURE

The order of the methods will be to the following for all participants:

Method 1: The participants will come to the study site. They will be informed about the study and give their written consent. Then, the test product will be issued to the participants with instructions to use them on the assigned test area (see application mode). The assignment of the test area will be done according to handedness of the participants. After the application of the test product with one hand, participants will wash their hands according to the washing procedure. 5 minutes after application, participants will wash the test area according to the washing procedure. The water of each washing step (hand and test area) will be caught separately in a jar and handled as described below (see investigational methods). The test product will be weighed before and after application.

Any remaining test product on the elbow and the hands will be removed using alcohol on a paper towel by the participants themselves.

[figure not shown]
Method 1

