Method 2: The participants will return to the study site and the test product will be applied with the applicator (see application mode). 5 minutes after application, participants will wash the test area according to the washing procedure. This will be repeated after 5 minutes. The water of each washing step (1st and 2nd washing of test area) will be caught separately in a jar and handled as described below (see investigational methods). The test product will be weighed before and after application.

Any remaining test product on the elbow and the hands will be removed using alcohol on a paper towel by the participants themselves.

Method 2

Method 3: The participants will return to the study site and the test product will be applied with the applicator (see application mode). 5 minutes after application, participants will wipe the test area with a paper towel. Afterwards, the test area and hands will be washed according to the washing procedure. The water of the washing step will be caught in a jar and handled as described below (see investigational methods).

The paper towels and test product will be weighed before and after application. Any remaining test product on the elbow and the hands will be removed using alcohol on a paper towel by the participants themselves.

Method 3

As a wash out period, a time frame of at least 2 days will be kept in between each method per participant. No carry over effect of the test product is to be expected due to this washout periods.

CLIMATIC CONDITIONS

During the investigation(s) room temperatures without additional air conditioning will be used.

TEST SCHEDULE

A scheme of the test procedure is given as appendix 1 to protocol.

INVESTIGATIONAL METHOD(S)

The following investigational method(s) will be performed:

TAKING OF WATER SAMPLES for lab analysis

- The water used for the washing sequence will be caught in a jar and will be stirred for 1 minute. Afterwards 3 water samples (approx. 100 ml) will be taken from different locations in the jar (top, bottom and in the middle) with tubes provided by the laboratory.
- A control sample of tap water only, collected prior to the product application, will also be analysed to prove the absence of diclofenac in the tap water used for washing.
- To minimize sample cross-contamination, a fresh pair of gloves will be worn by the technician for each participant.
- Water samples will be stored at room temperature until shipment.

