The investigator will decide which protocol deviations occurring in the study are assumed to be minor and major before data is analyzed. Valid participants will be defined as enrolled participants who will have finished the study without major deviations from the protocol and who will not have withdrawn their consent. As this is an exploratory study no sample size calculation was performed. The sample size was chosen based on the experience of the study site with this type of study CCI

CCI

Missing data

No replacement of missing data will be performed and the affected assessments will be regarded as lost for analysis.

Demographic data

Demographic variables (age, gender) will be given for the analysis population. Data will be summarized using frequency distributions (number and percentage) for categorical/ordinal variables and mean, standard deviation and range for continuous variables.

Unblinding and derandomization

Not applicable.

Data cleaning

Data cleaning and documentation will be performed according to study sites SOP, performing back-end checks and manual inspections, making self-evident corrections, querying potential data issues, executing necessary data corrections or deletions, tracking queries until resolved, and reviewing corrected data.

Data listing

Raw data

Diclofenac concentration: The mean of all three repeated measurements by participant and water sample (W0X) will be calculated and used as raw data further analysis.

All raw data will be listed by parameter and water sample for valid participants only.

Descriptive data analysis

Summary tables

Descriptive statistics (n, mean, standard deviation, median, minimum, maximum, and 95 % confidence limits) will be given for raw data by parameter and water sample.

Figures

The mean values of raw data will be presented in bar charts with 95 % confidence limits by parameter and water sample.

Statistical data analysis

A significance level of 0.05 (alpha) will be chosen for statistical analysis. Due to the explorative character of this study, no adjustments for multiplicity will be performed.

Pairwise comparison of all water samples will be done by paired t-test on raw data for diclofenac concentration.

The computation of the statistical data will be carried out with a commercially available statistics software (SAS for Windows).

FINAL REPORT

The report will include the following:

PDF report:

Identification of study personnel

Any protocol deviations and/or additional remarks

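### The planned tests compare single jars, so the Method 1 total and the two-wash Method 2 total are never compared with another method's total

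*Combined protocol and SAP*

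**What the plan says.** The Objective sets the question at the level of the method: "The amount of diclofenac in the water will be assessed after three different washing methods, with and without use of an applicator".

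Collection is at the level of the jar, and the number of jars differs by method (Assessment Times, Test Procedure):

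- Method 1, application by hand, has two jars, W01 (hands) and W02 (elbow): "The water of each washing step (hand and test area) will be caught separately in a jar".
- Method 2, applicator, has two jars, W03 and W04: "The water of each washing step (1st and 2nd washing of test area) will be caught separately in a jar".
- Method 3, applicator then wiping, has one jar for both sites ("Method 3 = W05 (Hands and elbow").

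The analysis follows the jars. Type of Statistics lists "Comparison between all water samples". Under Analysis of Data, the analysis variable is the mean of three concentration measurements per participant and water sample. Listings, summary tables and bar charts are by water sample. The only test is: "Pairwise comparison of all water samples will be done by paired t-test on raw data for diclofenac concentration". Alpha is 0.05, with no multiplicity adjustment.

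No visible text defines W01+W02, W03+W04, an amount (concentration times volume) or a contrast between methods. The Final Report section mentions a listing of calculated values but does not say what these are. Some text after the sample size statement is blacked out; nothing visible suggests that it defines a method total.

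**The concern.** W05 is the whole of Method 3, but it is tested only against parts of Methods 1 and 2. Hands plus elbow (W05) against hands alone (W01) or elbow alone (W02) is not like with like, and the mismatch tends to make Method 3 look worse. Methods 1 and 2 are compared only through four part-against-part tests, which need not agree with the order of the totals.

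The report will carry these p-values together with an interpretation of the data. A significantly higher W05 could then be read as more diclofenac in the water under Method 3 when its total is lower.

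**Working it through.** The plan gives no power or sample size figure to reproduce.

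**Inputs from the documents.** Five jars; about 30 completers (Study Population); alpha 0.05, taken as two-sided because sidedness is not stated; 2 L of rinse water per wash (Washing Procedure).

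**Inputs assumed.** Jar means, hand/elbow split, first-wash share, coefficients of variation (CV), within-person correlation and equal jar volumes. The documents give none of the first five and do not fix the last.

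**1. Count of tests.** 5 × 4 / 2 = 10. Two are within a method (W01 v W02, W03 v W04). Eight set a single jar of one method against a single jar of another. None uses W01+W02 or W03+W04.

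**2. A lower total that looks higher.** Let the Method 1 total be T, split 40/60, with volume V in every jar. Then W01 = 0.4T/V and W02 = 0.6T/V. If Method 3 truly releases 40% less, W05 = 0.6T/V.

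- W05 / W02 = 0.6 / 0.6 = 1.0
- W05 / W01 = 0.6 / 0.4 = 1.5

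In simulation (lognormal, n = 30, between- and within-person CV 30%), W05 differs significantly from W01 in 99.8% of studies, W02 v W05 rejects in about 6%, and a paired test on totals detects the reduction in 100%.

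**3. The same jar results from opposite truths.** Jar means in mg/l, 2 L per jar, within-person correlation 0.3, CV 20% to 50%:

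| Scenario | W01 | W02 | W03 | W04 | Method 1 total | Method 2 total |
|---|---|---|---|---|---|---|
| A | 10 | 10 | 15 | 1 | 2 × 20 = 40 mg | 2 × 16 = 32 mg |
| B | 10 | 10 | 20 | 4 | 2 × 20 = 40 mg | 2 × 24 = 48 mg |

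Both scenarios give W03 > W01, W03 > W02, W04 < W01 and W04 < W02, each significant in at least 93% of runs. Method 2 is lower in A and higher in B. Tests on totals separate them: Method 1 > Method 2 in 68% to 100% of runs in A, and Method 1 < Method 2 in 52% to 99.8% in B (CV 50% to 20%).

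With W05 = 13 mg/l in scenario A, Method 3 totals 2 × 13 = 26 mg against 40 mg for Method 1. W05 is nevertheless significantly higher than W01 and than W02 in about 63% to 100% of runs.

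**4. Rejection when method totals are equal** (n = 30, 40/60 split in Method 1 unless stated):

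| Test | First-wash share | CV | Rejects |
|---|---|---|---|
| W03 v W05 | 80% | 30% | 76% |
| W03 v W05 | 80% | 50% | 33% |
| W03 v W05 | 90% | 30% | 24% |
| W03 v W05 | 95% | 30% | 10% |
| W02 v W03, 20% on hands | 80% | 30% | 4% |

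W01 v W05 stays at 99% to 100%. Tests on totals reject in about 5%, which is alpha by construction.

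**The case against.** **The jar tests are not empty.** A reader might infer that they can never show the order of the methods. That goes too far. At equal volumes, W05 significantly below W01 or W02 implies a Method 3 total below Method 1, and W05 below W03 implies one below Method 2. If Method 2 is defined by its first wash alone, its contrast with Method 3 is already the planned W03 v W05 test. This stands.

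**Several jar contrasts are useful in themselves.** W02 v W03 compares the elbow wash five minutes after application by hand and by applicator. W03 v W05 compares applicator use without and with wiping; W05 includes the hands, but Application Mode says that the applicator is used without involving the hand. W03 v W04 shows what a second wash adds. Dropping all ten tests would lose this. This also stands.

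**High rejection rates are not all false positives.** A reader might infer that the jar tests are significant almost always even when the methods are identical. Equal totals with unequal splits mean that the jar means truly differ, and the rates depend on splits and CVs that the documents do not give.

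**The 40% example needs equal volumes.** The Washing Procedure wording suggests a single 2 L rinse for hands and elbow in Method 3, but this is not explicit, and the wetting water is unmeasured. If each site received 2 L, W05 would be 0.6T/4 = 0.15T per litre, against 0.30T for W02 and 0.20T for W01: half of W02 and 25% below W01. The example would reverse. That limits the example, and it also shows that concentrations alone do not order the methods.

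**The study is exploratory.** It is open-label, with no hypothesis or power claim, and it states openly that it compares water samples. Totals could be computed later from the listed concentrations if volumes were known. This lowers the severity. It does not make the planned tests answer the objective.

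**Conclusion.** The concern holds in a limited form. No planned test compares the Method 1 total, or the two-wash Method 2 total, with another method's total, so the tests do not in general identify which method puts less diclofenac into the water. That follows from the design of the tests and needs no assumption about variability.

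The size does rest on assumptions. The reversal in step 2 needs equal jar volumes and a 40/60 split. Under equal totals, W01 v W05 rejects in nearly every study, while W03 v W05 ran from about 10% to 76% over the combinations tried. The documents do not support a claim that every result pattern misleads, or that every jar test rejects almost always.

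Severity: should be fixed. The study is exploratory and states no hypothesis, but these tests are its only inferential output and the objective is stated per method.

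**What to change.** In Analysis of Data, define for each participant and method a total amount in mg: the sum over that method's jars of mean concentration × collected volume.

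- M1 = W01 + W02
- M2 = W03 + W04, with W03 alone as a stated second version
- M3 = W05

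Make the paired contrasts M1−M2, M1−M3 and M2−M3 the main comparisons, and state which version of M2 each uses. Add the totals to the summary tables and figures. Keep the jar-level results as secondary or descriptive, including W02 v W03, W03 v W05 and W03 v W04.

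The cost is one derived variable, some wording, and one new data item. The collected volume of each jar must be recorded, because the wetting water is not fixed. The Washing Procedure should also state whether Method 3 uses one 2 L rinse for both sites or one for each.
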